#### *Assessing non-response bias*

We will conduct response rate analysis for each primary outcome of interest to assess non-response bias and adjust for threats to internal validity. Using data from the Applicant Characteristics Survey, we will look at demographics (race, ethnicity, age, education level) and primary reason for joining the program among participants who fall into each of the following categories: 1) non-respondents who answered no surveys after the ACS, 2) respondents who completed a pre-survey only, and 3) respondents who completed both a pre- and follow-up survey (complete case).

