- **Goal 3 – Provide job readiness/placement and other supportive follow up services as secondary services to participants:** Candidates who receive job readiness/placement and other support services will understand that they will receive services that will help them obtain and maintain ongoing employment. The ongoing follow up support is important to

ensure that participants will increase their ability to financially provide for their children and families.

- **Goal 4 - Conduct Continuous Quality Improvement (CQI) to ensure full implementation of RISE services to both study groups:** Reports prepared and presented to the CQI Team by evaluators will use a series of performance indicators to track key outputs over time to identify any Fresno Fatherhood services that is delivered to participants that might fall short of the intended amounts to be offered (i.e., fidelity standards) and received (i.e., dosage thresholds). The CQI Team will then work with project staff to develop and implement performance interventions to address any outputs that need improvement to ensure the services offered to and received by participants meet the intended amounts by the end of each program year.

Desired Outcomes: Outcomes specified in the logic model theorize the primary and secondary outcomes that are desired for participants in each study group after they receive Fresno Fatherhood *primary and secondary services*. Secondary outcomes are the improved attitudes and expectations that indicate and reflect participant engagement in parenting, co-parenting, and financial stability. Primary outcomes are the healthy behaviors exhibited by participants for parenting, co-parenting, and economic stability that ultimately define the benefits of Fresno Fatherhood program participation. Outcomes specified in the logic model are confirmatory since it is expected that participation in the Fresno Fatherhood curriculum will result in positive increases in primary and secondary outcomes related to parenting, co-parenting, and financial stability.

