9.4. ENSURING AND MONITORING DATA COLLECTION

Describe plans for training data collectors and for updating or retraining data collectors about procedures. Detail plans to regularly review data that have been submitted and to assess and swiftly address problems.

This evaluation will utilize both post-program surveys (completed at the completion of core programming) and follow-up surveys collected one year after enrollment / baseline. The methods for these data collections differ. The primary driver for post-program survey completion is high rates of program retention. This data point will be collected during the last workshop session – after (but during the same session of) the completion of the nFORM post-program data collection. As such only those individuals who complete the program and who are at the data collection session will participate in the post-program data collection. All program participants, even those who do not complete the program, will be sent a 1-year follow-up survey if they consent to be part of the evaluation and have taken a baseline survey.

All program staff and evaluation staff will undergo a rigorous set of trainings to prepare for the evaluation. All staff receive an overview and introductory training to present the goals and objectives of the evaluation effort and its importance to the overall project. Next, all staff receive training on human subject's protection and are required to pass a certification test on the subject matter. All staff will also receive a detailed training on the details of the evaluation including the evaluation tools, timing, and data collection process and the role and importance of data accuracy.

In addition, the data manager and the primary local evaluation staff will undergo a rigorous training process to better understand the context of HMRF research, training on data collection procedures they will be responsible for, and training on the nFORM system and use of nFORM data in a CQI process. MER is creating networks of CQI data managers and Evaluation Project Managers across the 12 projects that we are evaluating so that all staff have access to experienced data managers and evaluation staff who have done this work previously. This training takes the form of weekly training sessions that are currently under way.

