### Identify study sample

The study sample includes participants who: 1) gave recorded informed consent to be part of the study, and 2) took both an entrance and exit survey (for attitudinal outcomes) or entrance and follow-up survey (for behavioral outcomes). The CONSORT diagram in Appendix C shows exclusion criteria and the anticipated size of the overall study sample. The analytic sample for particular outcome measures will vary based on missing data.

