#### Handling missing data

##### Outcomes

When creating the composite measures for our behavior and attitude outcomes, we will create a composite score by taking the average of multiple individual items. For these measures, our current plan is to use 20% as a threshold for allowable missing items, based on guidance from evaluation technical assistance resources. This plan is contingent on the final distribution of missing data in our data set. If participants have more than 20% of items missing for a given construct, the respondent will be assigned a missing value for that construct and will be excluded from the analytic sample for that outcome. We will not be imputing truly missing values for outcomes. To create a construct score, the average will divide by the number of non-missing values in the construct.

Participants who have not seen their child within the past month will have their parenting behavior responses set to “Never” (1) and will be included in the analytic sample for that outcome.

Data for the implementation outcomes could be missing as a result of programmatic data entry issues. For the sake of this evaluation, we assume that any primary or support services received by a participant are being accurately logged into nFORM, so a lack of documented attendance, service contacts, referrals, etc. is indicative of lack of services (i.e., a participant not receiving the program components as intended).

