#### **Analytic approach**

The main goal of this descriptive study is to assess pre-to-post change scores in the attitudinal outcomes listed above, and assess pre-to-one-year follow-up change scores in the behavioral outcomes listed above among program participants before and after primary workshops. We will use paired sample t-tests to assess the magnitude and significance of changes among program participants in the analytic sample for each outcome. For binary economic stability outcomes, we will descriptively report the percent of participants who opened a checking or savings account 1 year after enrollment, compared to the percent who had opened these accounts before the program. For binary employment outcomes, we will descriptively report the percent of participants who did not have a resume 1 year after enrollment, compared to the percent who did not have a resume before the program. We will adjust our p-values for multiple hypothesis testing and report the adjusted p-values in the appendix of the final report.

For the implementation analysis, program fidelity will be descriptively reported by the percentage of enrolled participants who receive: 1) any primary workshops, 2) employment supports, 3) substantive service contacts, 4) referrals. The program aims to provide all participants each of these four program components, so the percentage of participants who receive each of these will be compared to the 100% benchmark. Number of substantive service contacts per participant will also be compared to the benchmark of 8 SSCs set by OFA for FIRE grantees.

Exploratory analysis will examine how dosage varies by workshop characteristics (e.g., timing and length of sessions) and participant characteristics (e.g., age, employment status, relationship status).

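### The SAP promises to adjust for non-response, but R2 and R3 get only an unadjusted complete-case paired t-test, and the entrance scores of 1-year non-responders go unused

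*SAP*

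**What the plan says.** SAP, Assessing non-response bias, announces a response-rate analysis for each primary outcome, intended "to assess non-response bias and adjust for threats to internal validity". It then describes a comparison of "demographics (race, ethnicity, age, education level) and primary reason for joining the program" across three groups: fathers with no survey after the Applicant Characteristics Survey (ACS), fathers with a pre-survey only, and complete cases. R2 and R3 are covered, because Protocol section 3 states: "Primary outcomes are the healthy behaviors exhibited by participants for parenting, co-parenting, and economic stability".

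The rest of the SAP contains no adjustment for unit non-response:

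- Identify study sample limits behavioral outcomes to consented fathers who took both the entrance and the follow-up survey.
- Handling missing data, Outcomes: "We will not be imputing truly missing values for outcomes".
- Analytic approach: "We will use paired sample t-tests to assess the magnitude and significance of changes among program participants in the analytic sample for each outcome". Its one adjustment concerns multiplicity: "We will adjust our p-values for multiple hypothesis testing".

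The protocol has a wider population in view. R2 and R3 ask about program participants, and section 8.1 makes every program participant a study participant. Section 9.4 states: "All program participants, even those who do not complete the program, will be sent a 1-year follow-up survey", provided they consented and took a baseline survey.

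**The concern.** A reader who wants to know how attrition was handled will go to the non-response section and find a commitment to adjust. What follows is a table of ACS variables. The table omits the entrance outcome score, which is the variable most directly tied to the change being estimated and is already held for fathers who have an entrance survey but no follow-up.

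If fathers with low entrance scores answer more often, ordinary regression toward the mean among them appears as a program gain. If fathers with high scores answer more often, a real gain is masked. There is no comparison group to offset either effect. Protocol section 5 reads the pre-to-follow-up change as an upper limit on the benefit attributable to services, and selective response could undermine that reading.

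**Working it through.** **Is there an adjustment anywhere?** The SAP sections listed above contain no weights, response model, likelihood method, imputation or sensitivity analysis. Scoring parenting items as never for fathers who have not seen their child in the past month is a scoring rule for men who answered. It does not address men who did not answer.

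**When is the paired t-test biased for all consented fathers with a baseline survey?** Let Y0 be the entrance score, Y1 the 1-year score, S = 1 for response, and b the slope of Y1 on Y0. If response depends only on Y0 and the regression is linear,

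bias of the complete-case mean change = (b − 1) × (E[Y0 | S=1] − E[Y0]).

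Both factors must be non-zero. If response is unrelated to Y0, the second is zero. If change is unrelated to Y0 (b = 1), the first is zero.

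**Inputs.** The documents supplied give no response rate, SD, correlation or bias figure (Appendix C is not among them), so there is no planned figure to reproduce. The inputs below are assumptions.

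- Fathers: 389. This is 63 in year 1 plus 125 a year (Protocol section 1) over the 953 days from an assumed year-1 end of 9/30/2021 to the end of study enrollment on 5/10/2024: 63 + 125 × 953/365.25 = 389.
- Scores standard normal at both waves, correlation 0.5 (so b = 0.5), true mean change 0.
- Response 80%, 60% or 50%, logistic in Y0, with slope −0.25 or −0.5 in log-odds per SD.

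**One case by hand: 60% response, slope −0.5.** Integrating the response model over the normal distribution puts responders' mean entrance score 0.19 SD below the overall mean. Bias = (0.5 − 1) × (−0.19) = +0.095 SD. The SD of change is √(2 × (1 − 0.5)) = 1, and 0.6 × 389 = 233 fathers respond, so the SE is 1/√233 = 0.0655. The ratio is 0.095/0.0655 = 1.45, and the chance of two-sided rejection at 5% is about Φ(1.45 − 1.96) = 0.305. Simulation gives 30%.

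**Simulation, 4,000 trials per case:**

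| Response | Slope per SD | Bias, paired t-test (SD) | Paired t-test rejects a true null |
|---|---|---|---|
| 80% | −0.25 | +0.02 | 7% |
| 80% | −0.5 | +0.05 | 14% |
| 60% | −0.25 | +0.05 | 12% |
| 60% | −0.5 | +0.09 | 30% |
| 50% | −0.25 | +0.06 | 15% |
| 50% | −0.5 | +0.12 | 37% |

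Repeat runs move these rates by one or two percentage points. With slope 0 the rate is about 5%. With 60% response and slope +0.5 the bias is −0.095 SD. With correlation 0.7 (60%, −0.5) it is +0.057 SD, with 20% rejection. A two-wave likelihood estimate using all entrance scores has bias within 0.002 SD and rejects in about 5% of trials throughout.

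**Check of the two conditions**, with N = 63 + 4 × 125 = 563 and 70% response. At an odds ratio of 1.5 per SD and b = 0.5, the paired t-test gives −0.059 SD and 21% rejection. At b = 1 with the same odds ratio it is unbiased and rejects in 5.1%. At an odds ratio of 1.0 with b = 0.5 it is also unbiased.

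**Response driven by something else** (N = 389, 60% response, correlation 0.5, no true change):

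| Response depends on | Paired t-test | Two-wave likelihood estimate |
|---|---|---|
| A stable trait behind both scores (slope 0.5 per unit) | 0.00 SD, 5% | +0.05 SD, 12% |
| The 1-year score itself (slope 0.5) | +0.09 SD, 30% | +0.14 SD, 63% |

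**The case against.** The best defense is that the plan is open about what it does. The study is descriptive, Protocol section 1.2 labels R1 to R7 exploratory (although section 3 calls the outcomes confirmatory), and the SAP confines its tests to the analytic sample. A shift of 0.05 SD is modest beside the absence of a comparison group. This limits the seriousness of the point, but it does not supply the promised adjustment. Nor does it change the population that Protocol sections 8.1 and 9.4 describe.

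A reader might draw three stronger conclusions that the documents do not support:

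- *The paired t-test is biased whenever response depends on the entrance score.* It is not. Change must also vary with that score. On bounded 1-to-5 composites a slope of exactly 1 is unlikely, but the condition belongs in the statement.
- *Missing at random is the weaker assumption, so the mixed model should carry the conclusion.* Neither assumption contains the other. The last table shows two response patterns in which the model does worse than the paired t-test, and nothing in the documents says which pattern applies.
- *The $50 card draws in low scorers and so inflates the gain.* Protocol section 8.2 offers it to everyone who completes the 1-year survey. Nothing links it to the entrance score.

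**Conclusion.** The point holds as a gap between what the SAP promises and what it specifies. An adjustment for non-response is announced and none is defined. The entrance scores that could support one are left out of both the estimate and the response comparison. For all consented fathers with a baseline survey, the paired t-test is biased when 1-year response depends on the entrance score and change also varies with it. The illustrative size is 0.02 to 0.12 SD, with rejection of a true null in 7% to 37% of trials. Those figures rest on the assumed 389 fathers, correlation of 0.5, response of 50% to 80% and log-odds slopes of −0.25 to −0.5. Fewer fathers would lower the rejection rates: at 250, with 60% response and slope −0.25, the rate is 9% instead of 12%. The real direction and size are unknown. The evidence supports a second estimate reported alongside the first, and does not support replacing the paired t-test.

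**What to change.** 1. In Assessing non-response bias, add the entrance outcome score to the variables compared between fathers with a pre-survey only and complete cases.
2. In Analytic approach, report for R2 and R3, beside the paired t-test, a two-wave linear mixed model with unstructured covariance. Include every consented father with an entrance score and use the ACS variables as covariates. Keep the composite scoring rules the same for both estimates.
3. State that the model assumes response is missing at random given the entrance score and covariates, and that neither this assumption nor the paired t-test's contains the other.
4. State in advance that a conclusion on R2 or R3 will be described as sensitive to non-response if the two estimates disagree.

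Weights built only on the listed demographics would not in general remove this bias, because they leave out the entrance score. Deleting the promise to adjust would make the text consistent but would leave the data unused.

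The cost is SAP wording and a few hours of analysis, with no new data collection. The downside is a second estimate that may differ from the first and will then have to be explained.

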#### **Analytic approach**

The main goal of this descriptive study is to assess pre-to-post change scores in the attitudinal outcomes listed above, and assess pre-to-one-year follow-up change scores in the behavioral outcomes listed above among program participants before and after primary workshops. We will use paired sample t-tests to assess the magnitude and significance of changes among program participants in the analytic sample for each outcome. For binary economic stability outcomes, we will descriptively report the percent of participants who opened a checking or savings account 1 year after enrollment, compared to the percent who had opened these accounts before the program. For binary employment outcomes, we will descriptively report the percent of participants who did not have a resume 1 year after enrollment, compared to the percent who did not have a resume before the program. We will adjust our p-values for multiple hypothesis testing and report the adjusted p-values in the appendix of the final report.

For the implementation analysis, program fidelity will be descriptively reported by the percentage of enrolled participants who receive: 1) any primary workshops, 2) employment supports, 3) substantive service contacts, 4) referrals. The program aims to provide all participants each of these four program components, so the percentage of participants who receive each of these will be compared to the 100% benchmark. Number of substantive service contacts per participant will also be compared to the benchmark of 8 SSCs set by OFA for FIRE grantees.

Exploratory analysis will examine how dosage varies by workshop characteristics (e.g., timing and length of sessions) and participant characteristics (e.g., age, employment status, relationship status).

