1. PROGRAM SUMMARY

Please provide a brief summary of your grant project including the needs to be addressed, the services provided, and the population served.

The Fresno region of California, at both the city and county levels, is a region impacted by high rates of poverty and unemployment. Prior research suggests that poverty is often inextricably linked to high crime rates. High crime rates can then lead to high rates of incarceration, thereby contributing to chronic father absenteeism and the breakdown of healthy families. The purpose of the Fresno Fatherhood program is to employ a comprehensive and holistic healthy marriage, responsible parenting and economic stability education and related services to at-risk adult community fathers (i.e., 18 and older) who have children aged 24 years or younger and reside in areas of high poverty. While the program does not plan on serving only fathers who are housed in treatment facilities, non-custodial, or justice involved, the grantee (FAWIC) expects that many will have these characteristics.

The core services of Fresno Fatherhood include: healthy marriage, responsible parenting, and economic stability education and services. These services will be delivered by using a primary workshop focused on fatherhood skills using the National Fatherhood Initiative's 24/7 Dad evidence-based/evidence-informed curricula; job readiness services, including career exploration and planning; job-driven employment services, including development of skills tied to demand jobs in growth sectors of the local economy; job placement assistance; intensive case management and service navigation support; mentoring to encourage and support fathers in applying the knowledge and skills they acquire through the project; supplemental workshops focused on life skills, financial literacy and personal development; and referrals to a full array of support services through both grant-funded and leveraged resources. FAWIC will provide parenting and relationship instruction via a primary workshop to 63 fathers in year 1 and 125 annually in years 2-5.

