8. SAMPLE

8.1. TARGET POPULATION(S)

For each target population identified in Section 1.2, please describe the target population(s), and explicitly state whether the population(s) differs from those who will be broadly served by the grant. Describe how the target population will be identified. Explicitly state the unit of analysis (e.g., non-residential father, unmarried couple).

Description of Target Population	How is the population different from those who will be broadly served by the grant?	How will the target population be identified?	Unit of Analysis
Target population is community fathers (ages 18 and older), who have children ages 24 and younger and reside in communities with high rates of poverty.	No difference, all program participants will be study participants.	The sample will be identified and recruited by community partner referrals and program staff.	Community adult fathers

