9.3. METHODS OF DATA COLLECTION

If the evaluation will collect multiple waves of data, describe the timing of these waves below. When describing follow-up periods, specify whether the follow-up period will be post-baseline, post-random assignment, or post-program completion.

Wave of Data Collection (e.g., baseline, short-term follow-up, long-term follow-up)	Timing of Data Collection
Baseline	Collected immediately following informed consent and enrollment – during the orientation session or first workshop
Post-Test	Collected after the completion of core curriculum programming -during the last workshop session – approximately 4 weeks after enrollment.
1 year Follow-up (post-baseline)	Collected approximately one year after program enrollment/ baseline. Participants who did not complete the program will still be eligible for a follow-up survey as long as they consented to be in the study and took a baseline survey.

For each measure, describe how data will be collected detailing which data collection measures will be collected by which persons, and at what point in the programming or at what follow-up point.

Measure	Timing of Data Collection (baseline, wave of data collection)	Method of Data Collection	Who Is Responsible for Data Collection?	Impact Evaluations Only: Will Methods or Collection Procedures Differ by Study Group?	Administrative Data Only: Will data access require data sharing agreement?
Online Local Evaluation (OLLE) Baseline Survey	Baseline	Participant self-enters survey using online Qualtrics data collection platform	Case Manager and/or facilitator will proctor data collection and assist participants as necessary	N/A	N/A
nFORM Community Fathers Entrance Survey	Baseline	Participant self-enters survey using online nFORM data collection platform	Case Manager and/or facilitator will proctor data collection and assist participants as necessary	N/A	N/A
OLLE Post-Test Survey	Post-Test (approx. 4 weeks after enrollment)	Participant self-enters survey using online Qualtrics data collection platform	Case Manager and/or facilitator will proctor data collection and assist participants as necessary	N/A	N/A
nFORM Community Fathers Exit Survey	Post-Test (approx. 4 weeks after enrollment)	Participant self-enters survey using online nFORM data collection platform	Case Manager and/or facilitator will proctor data collection and assist participants as necessary	N/A	N/A

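### The paired t-tests take no account of workshop grouping; if fathers' changes are correlated within a workshop series, the p-values for the five tested composites are too low

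*SAP*

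**What the plan says.** The SAP's test of change is stated in one sentence under Analytic approach: "We will use paired sample t-tests to assess the magnitude and significance of changes among program participants". No workshop term, random effect or robust standard error is mentioned. The two binary outcomes (account and resume) are reported as percentages. That leaves at most five tested composites: parenting, financial and employment attitudes at exit, and parenting and co-parenting behaviors at one year. P-values will be adjusted for multiple testing, by a method that is not named.

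The Protocol describes group delivery. Its Program Summary says "These services will be delivered by using a primary workshop focused on fatherhood skills". Section 9.3 places baseline at orientation or the first workshop, and for the baseline and post-test surveys states that the "Case Manager and/or facilitator will proctor data collection and assist participants as necessary". On the post-test, section 9.4 says "This data point will be collected during the last workshop session". Section 8.1 gives the unit of analysis as "Community adult fathers".

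In the SAP, workshops enter only an exploratory analysis of "how dosage varies by workshop characteristics", not the outcome tests.

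**The concern.** Pairing deals with the correlation between one father's two measurements. It does nothing about correlation between different fathers. Fathers in the same series may share a facilitator, peers, calendar period and, at exit, the survey session and the person proctoring it. Any of these could make their changes resemble each other. The t-test would then count more independent information than the data hold.

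This matters because all seven outcome questions in Protocol section 1.1 ask whether participants show significant increases. For the tested composites, the p-value therefore largely determines the answer. The planned multiplicity adjustment does not help, because it starts from raw p-values that would already be too low.

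**Working it through.** **Inputs from the documents.** The service target is "63 fathers in year 1 and 125 annually in years 2-5", so 63 + 4 × 125 = 563 fathers. This is a target for services, not an analysed sample; the SAP says "The analytic sample for particular outcome measures will vary based on missing data". The documents as available state no significance level, sidedness, ICC, workshop size or number of series, so there is no planned figure to reproduce.

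**Assumptions.** Two-sided 5% level. Analysed fathers per series m = 4 to 15. ICC of change scores 0 to 0.05. Series of equal size.

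**Formulas.**
- Design effect: DE = 1 + (m − 1) × ICC.
- The true standard error is the t-test's standard error × √DE.
- True two-sided error = 2 × [1 − Φ(1.96/√DE)].

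**Worked case, m = 10 and ICC = 0.05.** DE = 1 + 9 × 0.05 = 1.45. √DE = 1.204. 1.96/1.204 = 1.628. True error = 2 × [1 − Φ(1.628)] = 10.4%.

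**True error over the range:**

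| m | ICC 0 | ICC 0.01 | ICC 0.02 | ICC 0.05 | DE at ICC 0.05 |
|---|---|---|---|---|---|
| 4 | 5.0% | 5.3% | 5.7% | 6.8% | 1.15 |
| 8 | 5.0% | 5.8% | 6.6% | 9.2% | 1.35 |
| 10 | 5.0% | 6.0% | 7.1% | 10.4% | 1.45 |
| 15 | 5.0% | 6.6% | 8.3% | 13.3% | 1.70 |

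At the top of the range the standard error is too small by a factor of √1.70 = 1.30.

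**Simulation check.** Change scores with zero true mean change were simulated for 300 fathers, 10,000 replicates per scenario. The ordinary t-test rejected in 5.8% (ICC 0.01) and 10.2% (ICC 0.05) of replicates with 30 series of 10. With 20 series of 15 it rejected in 6.4% and 13.3%. These agree with the formula. A t-test on the series means, which respects the grouping, rejected in 4.8% to 5.4% in every scenario.

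**Are there enough series for a robust standard error?** If 8 to 15 fathers attend each series (an assumption), 563 fathers make about 563/15 ≈ 38 to 563/8 ≈ 70 series. That is workable with a small-sample correction. The number analysed will be lower, because study enrollment closes before the program ends and some surveys will be missing.

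**The case against.** The strongest objection is that nothing in the documents shows the correlation exists. There is no ICC and no workshop size, and it is not stated whether groups are fixed or rolling. At ICC 0 the planned test is correct. This stands, and it makes the point conditional.

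Second, m counts fathers analysed, not fathers attending. Attitude analyses need both entrance and exit surveys, and exit surveys come only from those present at the last session. If half of 8 to 15 attenders are analysed, m is about 4 to 8 and the error is about 5.3% to 9.2% for ICC 0.01 to 0.05. This stands, and it is why the range above starts at 4.

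Third, Protocol section 3 makes behaviors the primary outcomes, and these are measured a year after enrollment, individually, online or by phone, with non-completers eligible. Services also include case management, job placement and mentoring, which may dilute any workshop effect. This stands too: the exit attitudes are the main exposure.

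Fourth, the study is single-arm and descriptive. Section 1.2 labels every outcome question exploratory, although section 3 calls the outcomes confirmatory. The lack of a comparison group limits interpretation more than the standard error does. That lowers the stakes but does not justify a test whose independence assumption is doubtful and cheap to relax.

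Two stronger readings should be resisted. A reader might infer that a 5% error rate is definitely exceeded; no level is stated and the inflation depends on an unknown ICC. A reader might also infer that planned confidence intervals are too narrow; the SAP describes tests and p-values and plans no intervals.

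**Conclusion.** The point holds conditionally. The SAP's tests assume independence between fathers, while the delivery of the curriculum and the exit measurement give a clear reason to doubt it. Any positive within-series ICC of change scores makes the p-values too low. Under the stated assumptions, the true error rate at a nominal 5% lies between 5% and about 13%. The upper end needs both 15 analysed fathers per series and an ICC of 0.05. The three exit attitude composites are the most exposed and the two one-year behavior composites less so. The binary outcomes are unaffected because they are not tested. The change is worth making because the remedy is inexpensive and reporting the ICC would show whether the problem is real.

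**What to change.** Amend the SAP's Analytic approach as follows, before the outcome tests are run:

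- State the significance level and sidedness.
- Estimate the same mean change for each composite, with cluster-robust standard errors by workshop series and a small-sample correction.
- Assign each father to the series he first attended, using nFORM attendance records.
- Treat each father who attended no workshop as a separate cluster of one. Pooling all non-attenders into one cluster would impose a correlation on men who shared no workshop.
- Report the ICC of change scores for each composite.
- Compute the multiplicity-adjusted p-values from these tests.

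The estimated mean change is the same as under the t-test. A random intercept for series is an alternative, but it can shift the estimate slightly when series differ in size.

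The cost is analytic and needs no new survey data. The SAP assumes that services received are accurately logged in nFORM, so attendance should be available. However, the documents show no series identifier; one must be derived, with the first-attendance rule covering fathers who move between series. If the ICC is above zero, standard errors and p-values become somewhat larger.
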